## 2) Severity

Adverse event severity will be classified using the following categories.

Event	Mild	Moderate	Severe
Vaccination site redness	long axis $\leq$ 2.0 cm	long axis $>$ 2.0 cm, $\leq$ 5.0 cm	long axis $>$ 5.0 cm
Vaccination site swelling			
Vaccination site induration			
Vaccination site pain	Whimpers when the vaccination site is touched	Cries when the vaccination site is touched	Cries when vaccinated arm is moved
Pyrexia	$\geq 37.5^{\circ}\text{C}$ , $< 38.5^{\circ}\text{C}$	$\geq 38.5^{\circ}\text{C}$ , $< 40.0^{\circ}\text{C}$	$\geq 40.0^{\circ}\text{C}$
Decreased appetite	A little decreased	Half or less of normal	Hardly eats at all

Adverse event severity other than that described above will be classified using the following categories.

1. Mild: No effect on the subject's activities of daily living
2. Moderate: The event impacts the subject's activities of daily living
3. Severe: The event prevents the subject from performing activities of daily living

## 3) Seriousness

The seriousness of adverse events will be classified using the following categories.

1. Not serious: Anything other than 2 below
2. Serious: Any of a) through f) below
  - a) Death
  - b) Life-threatening
  - c) Necessitates admission to a hospital or clinic for treatment, or the prolongation of a hospital stay
  - d) Disability
  - e) A serious outcome comparable to those listed in a) through d) above
  - f) Congenital disease or abnormality in the next generation

## 4) Causal relationship to the investigational product

For events other than vaccination site reaction, which are pre-specified adverse events, the (sub)investigator will assess whether or not there is a "reasonable possibility" that the investigational product caused the adverse event in question. This assessment is made in consideration of the underlying disease, concomitant medical diseases, and other aspects of the natural course of the primary disease, concomitant therapies risk factors and factors other than the investigational product, and the temporal relationship between investigational product dosing and adverse event onset. If it is unknown or cannot be determined whether or not there is a reasonable possibility, then it will be concluded that there is a reasonable possibility. For all vaccination site reactions (vaccination site redness, swelling, induration, and pain), which are pre-specified adverse events, the causal relationship to the investigational product will be classified as "there is a reasonable possibility." Adverse events for which it is thought "there is a reasonable possibility" of there being a causal relationship with the investigational product are considered adverse drug reactions.

1. Reasonable possibility
2. No reasonable possibility

5) Outcome

The outcomes of adverse events will be classified using the following 6 categories.

1. Recovered
2. Recovering
3. Did not recover
4. Recovered, but with sequelae
5. Death
6. Unknown

6) Day of outcome

The day of outcome will be classified according to the following criteria.

Recovered	: The day of resolution. However, if the day on which the subject recovered cannot be identified, then the day of outcome will be the day on which the outcome was confirmed or determined.
Recovering	: The day on which it was confirmed or determined that the subject was recovering.
Did not recover	: The day on which it was confirmed or determined that the subject had not recovered.
Recovered with sequelae	: The day on which it was confirmed or determined that sequelae were present.
Death	: The day of death. However, if the day of death cannot be determined, then this will be the day on which the death was confirmed or determined.
Unknown	: The day of death if the subject died due to a cause other than the adverse event in question and the outcome was unknown. Otherwise, this will be the day on which the outcome was confirmed or determined.

7) Follow-up Investigation

Adverse events that occur during the safety assessment period will be followed until 28 days after Post-vaccination Examination 1 or Post-vaccination Examination 2, and the findings recorded in the case report form. Furthermore, if there is a valid reason for stopping the investigation partway, then this reason will be entered in, for example, the source documents, and the follow-up investigation will be concluded. The day of the outcome that is recorded on the case report form for adverse events that are recovering or have not recovered at the end of the follow-up investigation period will be considered the day of the final observations in the follow-up investigation period. For adverse drug reactions that are recovering or have not recovered at the end of the follow-up investigation period, the subsequent courses of these reactions will be investigated.

Furthermore, serious adverse events that occur in the period from Post-vaccination Examination 1 until the vaccination of the fourth dose of the investigational product will be followed until 28 days after Post-vaccination Examination 2.

(5) Information recorded in the case report form

When an adverse event occurs, the (sub)investigator will record the following information in the

adverse events section of the case report form: name of the adverse event;\* if the event is a pre-specified adverse event, then the site of onset; if the adverse event is “pyrexia,” then the highest axillary body temperature measured during the period of pyrexia emergence; day of onset; severity; seriousness; causal relationship to the investigational product; actions taken with respect to the investigational product; a description of other actions taken, if any (e.g., names of drugs or therapies); outcome; and date of outcome. In addition, for immediate reactions, the presence or absence of any such reactions, as well as the details thereof, will be confirmed, and the information recorded in the immediate reactions section of the case report form.

\*: The adverse event terms will conform to the following criteria.

- As a rule, the diagnosis term will be used.
- If the diagnosis term is unclear, the symptom name will be used.
- If multiple symptoms emerge, and if they indicate a single diagnosis term, then this diagnosis term will be used.

Surgical procedures, etc. will not be considered adverse events; if an illness and/or symptom requiring a surgical procedure, etc. is confirmed, then this will be considered an adverse event.

Furthermore, for vaccination site reactions (vaccination site redness, swelling, induration, and pain), which are pre-specified adverse drug reactions, that have been recorded in the e-Diary by the subject’s legal guardian, the study sponsor will establish the date of onset, date of outcome, and outcome of the adverse event in accordance with the criteria shown below. Further details are provided in separate written procedures.

1) Definition of date of onset to date of outcome

From the first day after vaccination with the investigational product on which “Yes” was entered for the vaccination site reaction until the last day “Yes” was entered.

2) Outcome definitions:

(a) Redness, swelling, and induration

Recovered: When “No” was entered for vaccination site reactions

Recovering: When the last long axis value entered is less than the maximum value

Did not recover: When the last long axis value entered is equal to or more than the maximum value

(b) Pain

Recovered: When “No” was entered for vaccination site reactions

Recovering: When the last severity rating entered indicates improvement compared to the worst rating entered

Did not recover: When the last pain rating entered indicates no improvement compared to the worst rating entered

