### 9.2.4.2 Adverse Events

An adverse event is any clinically undesirable or unintended sign (including clinically significant test value abnormalities), symptom, or disease that occurs during the safety assessment period following vaccination with the investigational product, regardless of whether or not it is causally related to the investigational product.

Furthermore, vaccination site reactions (redness, swelling, induration, pain) and systemic reactions (pyrexia, irritability, crying, decreased appetite, decreased sleep, increased sleep), which are reactions that are specific to vaccination, that occur in the period up through Day 14 after vaccination with the investigational product will be considered pre-specified adverse events. Vaccination site reactions to other

vaccines that were administered at the same time will be considered normal adverse events, and will not be considered pre-specified adverse events. Axillary body temperature  $\geq 37.5^{\circ}\text{C}$  will be handled as the adverse event “pyrexia.” In addition, adverse events that occur within 30 minutes after vaccination with the investigational product will be considered immediate reactions.

(1) Symptoms or diseases

The (sub)investigator will confirm the presence or absence of adverse events based on the contents of the e-Diary that has been filled out by the legal guardian, as well as by questioning of the legal guardian and observation of the subject.

(2) Clinical laboratory test abnormalities

The (sub)investigator will handle as an adverse event any event that is judged to be a clinically significant abnormality.\*

\*: A “clinically significant test value abnormality” will be determined based on the following criteria.

- When there is a relationship to a clinical sign or symptom

However, if these symptoms or signs have been reported as separate adverse events, then there is no need to handle this test value abnormality as an adverse event.

- When a medical or surgical treatment has been administered for the test value abnormality in this clinical laboratory tests
- When the investigational product vaccination method has been changed (e.g., a change in the dose, treatment interruption, treatment discontinuation) because of the test value abnormality
- When the (sub)investigator determines for some other reason that the finding is a clinically significant abnormality

(3) Safety assessment period

1) Cohort 1

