#### 17.5 Handling of e-Diary

Each subject's legal guardian will enter into the subject's e-Diary the information for the parameters specified in Section 9.2.4.1 every day until Day 14 after vaccination with the investigational product and also, as a rule, until the subject's symptoms have resolved for subjects who symptoms have not resolved by Day 14 after vaccination with the investigational product. The (sub)investigator or a clinical research coordinator will check the information that the subject's legal guardian entered into the e-Diary, and if there are any doubts about the information that has been entered, the investigator or clinical research coordinator will promptly confirm this information with the subject's legal guardian, and if there are any parts of the e-Diary that have not been filled out, will ask the subject's legal guardian to enter the symptoms to the extent possible.

In this study, of the safety assessment parameters, the presence or absence of vaccination site reactions, and the size or severity thereof, will be assessed based on the data that are entered into the e-Diary by the subject's legal guardian. Other adverse events will be assessed by the (sub)investigator based on both the information that has been entered into the e-Diary by the subject's legal guardian and the (sub)investigator's examination of the subject.

The principal investigator will store a copy of the e-Diary on a recording medium such as a CD-R provided by the study sponsor.

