7.6.1.3. Incidence of Solicited Adverse Events by Number of Doses

Analysis population(s): Safety analysis set

Analysis parameter: Adverse events and reactions that are considered solicited adverse events

Analysis method: For each number of doses, for each group, and for each MedDRA/J SOC and PT, the numbers and proportions of subjects experiencing each type of event will be tabulated by event category (solicited adverse events, immediate reactions).

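### The diagnosis-term rule does not exempt the pre-specified systemic reactions and conflicts with the pyrexia rule, so all-cause solicited systemic rates may be understated

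*Protocol*

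**What the plan says.** Protocol 9.2.4.2 lists the vaccination site reactions and six systemic reactions (pyrexia, irritability, crying, reduced appetite, less sleep, more sleep) "that occur in the period up through Day 14 after vaccination with the investigational product will be considered pre-specified adverse events". No restriction by cause is attached. The same section says that an axillary temperature of 37.5 °C or more "will be handled as the adverse event" pyrexia.

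The footnote to 9.2.4.2(5) governs the name entered in the case report form for every adverse event: "As a rule, the diagnosis term will be used", and "If multiple symptoms emerge, and if they indicate a single diagnosis term, then this diagnosis term will be used". The sentence it annotates mentions pre-specified events, but the footnote does not exempt them. That same sentence asks for the peak temperature only when the event is pyrexia.

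Protocol 17.5 splits the sources. Site reactions "will be assessed based on the data that are entered into the e-Diary" by the guardian. For the rest, "Other adverse events will be assessed by the (sub)investigator based on both the information that has been entered into the e-Diary" and on examination. Protocol 9.2.4.1 nevertheless collects temperature and each of the other five systemic reactions daily in the e-Diary.

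The Cohort 1 and Cohort 2 SAPs (7.6.1.1 to 7.6.1.3) tabulate by event category and, in 7.6.1.2 and 7.6.1.3, by MedDRA/J SOC and PT. The analysis parameter in 7.6.1.3 is "Adverse events and reactions that are considered solicited adverse events". Neither SAP defines solicited (the protocol's word is pre-specified), and neither plans a table from raw e-Diary temperatures or systemic entries.

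**The concern.** Take an infant with fever, crying and poor appetite on Day 5 whom the investigator judges to have a cold. Under the pre-specified list this infant has three solicited events. Under the naming footnote the infant has one event, a cold, and leaves all three solicited rows. Both records comply with the protocol, and nothing says which is meant.

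Where the footnote is applied to a solicited symptom, the solicited count can only fall. How far it falls depends on how readily each investigator names an infection, so rates could differ between sites for reasons unrelated to the vaccine. Fever grading is exposed too, because the peak temperature reaches the case report form only if the event is called pyrexia. Adverse events and adverse drug reactions are the only safety endpoint (Protocol 5.4.2), for a product with no earlier clinical study (Protocol section 1(3)).

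**Working it through.** The plan states no expected systemic reaction rate and no relabelling share, so there is no figure to reproduce. The check has two parts.

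**Which rule reaches which event**

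| Event through Day 14 | Rule keeping it as its own event | Does the diagnosis-term footnote also apply? | Recovered from the e-Diary? |
|---|---|---|---|
| Site reactions | Pre-specified list; assessed from the e-Diary (17.5) | No practical effect | Yes |
| Pyrexia | Pre-specified list, plus the 37.5 °C rule | Yes: direct conflict | No |
| Other five systemic reactions | Pre-specified list only | Yes: no precedence stated | No |

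The sponsor's derivation of dates and outcomes at the end of 9.2.4.2(5) also covers site reactions only.

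**Size, under stated assumptions**

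Let p be the true proportion of subjects with the reaction. Let f be the share of those subjects for whom every episode in the period is recorded only under a diagnosis. *Every episode* matters because a repeated PT is counted once per subject per period (Cohort 1 SAP 6.4.1, Cohort 2 SAP 6.4); one episode recorded as itself keeps the subject in the count.

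- Reported rate = p × (1 − f); loss = p × f.
- Assumed p = 40%: f = 0, 10%, 20%, 30% gives 40%, 36%, 32%, 28%.
- Loss for f from 0 to 30%: 0 to 3 points at p = 10%, 0 to 9 at p = 30%, 0 to 15 at p = 50%.

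Against sampling error in Cohort 2 (170 per group, Clopper-Pearson 95% interval): an assumed true 30% is 51/170 (23.2% to 37.5%). With f = 30% it becomes 36/170 = 21.2% (15.3% to 28.1%). At that extreme the reported rate falls below the lower limit of the first interval; with f = 10% (46/170 = 27.1%) it does not.

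**Difference between arms**

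- If vaccine-caused and background reactions are relabelled alike, with the same f in both arms, a true 10-point difference becomes 10 × (1 − f) = 9, 8 or 7 points at f = 10%, 20%, 30%.
- If f differs, for example 20% against 10% with true rates of 50% and 40%, the difference is 50 × 0.8 − 40 × 0.9 = 40 − 36 = 4 points instead of 10.
- If only background illness is relabelled, the difference does not shrink. Assume an independent 10% background in both arms and a 15-point difference in vaccine-caused fever. Counting every fever shows 15 × (1 − 0.10) = 13.5 points; dropping only the background fevers shows 15.

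**The case against.** The strongest reply is that 9.2.4.2 is the specific rule and the footnote the general one, softened by its opening words. The pre-specified list names all six systemic reactions, the 37.5 °C rule is explicit, peak temperature is requested for pyrexia, and the severity table in 9.2.4.2(4) has its own rows for pyrexia and reduced appetite. Read that way, f = 0 for fever and probably for the rest. The eCRF Entry Manual mentioned in Protocol 17.3, which is not among the documents reviewed, may give these reactions their own fields.

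This stands in part. A reader might infer that the plan replaces fever with a diagnosis, or that solicited rates are understated as a matter of fact. The text supports neither: fever is the best protected of the six, and nothing shows how often relabelling happens. But the pre-specified list classifies events without saying that it overrides the naming rule, so the conflict remains on the page.

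Two limits on scope also stand. Cohort 1 SAP 7.6.1.4 is not implemented, and Cohort 2 SAP 7.6.1.4 covers adverse drug reactions only, where a symptom put down to a cold and judged unrelated is left out anyway. And it is partly a matter of preference whether diary entries alone should count a systemic reaction without the investigator's assessment.

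**Conclusion.** The point holds as an unresolved conflict with a known direction and an unknown size. The diagnosis-term rule has no exemption for pre-specified systemic reactions; it contradicts the 37.5 °C rule for pyrexia, and precedence is unstated for the other five. Because these reactions are not taken from the e-Diary, the all-cause solicited tables in 7.6.1.1 to 7.6.1.3 of both SAPs may be understated and may vary by site. The loss is p × f. The figure of 40% falling to between 40% and 28% rests wholly on an assumed rate and an assumed f of 0 to 30%; f = 0 is possible, and is the literal result of the 37.5 °C rule for pyrexia.

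A reader might also infer that an excess with BK1310 would be hidden. That does not follow. The difference shrinks only if vaccine-caused reactions are relabelled too, or if relabelling differs between arms. Protocol 13.3.3 and Cohort 2 SAP 7.6.1.1 plan per-group proportions and intervals, with no between-arm safety difference.

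**What to change.** Reconcile the two parts of Protocol 9.2.4.2: state in 9.2.4.2(5) that the pre-specified systemic reactions are exempt from the diagnosis-term rule.

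In both SAPs:
- define solicited events as the protocol's pre-specified events;
- count an all-cause solicited systemic reaction through Day 14 whenever the e-Diary or the investigator records it, including any temperature of 37.5 °C or more, whatever diagnosis is also recorded;
- grade pyrexia from the highest recorded temperature;
- keep the diagnosis as an additional unsolicited event;
- keep the causality assessment for the adverse drug reaction tables.

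The cost is one sentence in the protocol (with the entry manual aligned) and a short derivation paragraph in each SAP; the data are already collected under Protocol 9.2.4.1. The downside is that fevers and symptoms from intercurrent illness add background to both arms, which raises the all-cause rates and, as the 13.5-against-15 example shows, can slightly dilute a difference. The adverse drug reaction tables remain the place to read rates restricted by causality.

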## 10. Assessment Methods and Criteria

### 10.1 Efficacy

(1) The antibody titer measurement methods and seroprotection rate criteria

Measurement Parameters		Measurement Method	Reference Value
Hib	Anti-PRP antibody concentration	Enzyme-linked immunosorbent assay (ELISA)	$\geq 1 \mu\text{g/mL}$ 
			$\geq 0.15 \mu\text{g/mL}$ 
Diphtheria	Anti-diphtheria antibody concentration	Neutralization method	$\geq 0.1 \text{ IU/mL}$ 
Pertussis	Anti-pertussis antibody concentration	Enzyme-linked immunosorbent assay (ELISA)	$\geq 10.0 \text{ U/mL}$ 
	Anti-FHA antibody concentration		$\geq 10.0 \text{ U/mL}$ 
Tetanus	Anti-tetanus antibody concentration	Indirect agglutination (KPA)	$\geq 0.01 \text{ U/mL}$ 
Polio	Attenuated anti-poliovirus antibody titers* (types 1, 2, and 3)	Neutralization method	$\geq 8\text{-fold}$ 

\*: Sabin strains

The proportions of subjects with the aforementioned reference antibody titers following vaccination with the investigational product will be calculated.

Seroprotection rate (%) =

[Number of subjects with antibodies]/(Number of subjects evaluated for efficacy)] x 100

### 10.2 Safety

Adverse events and adverse drug reactions (for details, see “9.2.4.2 Adverse Events”)

## 11. Ensuring Subject Safety

### 11.1 Handling of Serious Adverse Events

If serious adverse events occur during the treatment period, the (sub)investigator will immediately provide the subject with appropriate treatment irrespective of the presence or absence of a causal relationship to the investigational product.

In the event of a serious adverse event, the (sub)investigator will immediately notify a monitor (in writing, as a rule) and submit detailed information in writing within 7 days after notifying the monitor. In addition, the principal investigator will immediately report any such serious adverse events to the director of the study site.

#### Serious Adverse Event Definition

- (1) Death
- (2) A life-threatening event
- (3) An event that necessitates admission to a hospital or clinic for treatment, or the prolongation of a hospital stay
- (4) Disability
- (5) An event with a level of seriousness comparable to those listed in (1) through (4) above
- (6) A congenital disease or abnormality in the next generation

### 11.2 Clinically Significant Adverse Event

In this study, no “clinically significant adverse event” designation has been established.

### 11.3 Informing the Subject’s Other Doctors

The (sub)investigator will check whether or not the subject is being treated outside the context of this study both at written informed consent obtainment and during the study. If a subject is being treated by another doctor, this doctor will be informed, with the legal guardian’s consent, of the subject’s participation in this study. In addition, the (sub)investigator or a clinical research coordinator will give the legal guardian a study participation card or the like and instruct the legal guardian to present it to other hospitals or departments to inform other doctors of the subject’s participation in the study.

## 12. Subject Study Discontinuation Criteria and Procedures

### 12.1 Subject Discontinuation Criteria

If any of the following discontinuation criteria are met, the subject will be discontinued from the study.

- (1) If the legal guardian requests discontinuation.
- (2) If it is determined that the subject is clearly ineligible to participate in the study.
- (3) If the (sub)investigator determines that it would be difficult for the subject to continue the study because of the emergence of, for example, an adverse event.
- (4) If the (sub)investigator determines that the subject should be discontinued from the study for some other reason.

